Stepwise regression analysis will be performed to model the relationship between pre-randomisation factors and demographics on observed outcomes at 15 months. Interaction terms with the allocation arm will be included in the analysis, and a significance level of 0.1 will be used to determine which factors are to be included in the regression model. Pre-

randomisation factors will include pupil sex, FSM status and ethnicity. This analysis will be augmented by an additional analysis including participants in the intervention arm using the same pre-randomisation factors, process measures of intervention delivery, and staff changes in perceptions of trauma-informed care.

Table 6 sets out the statistical analysis for each outcome by level.

Table 6 Statistical analysis by outcome and level

Outcome	Level	Model	Covariates
Primary outcome Externalising behaviour Secondary outcomes Internalising behaviour Non-psychotic psychological distress Well-being Sense of connectedness Exclusions, suspensions and attendance at individual (CYP) level	CYP	Multi-level model	Pre-treatment scores of outcomes at CYP level Demographic factors (sex, FSM status) at CYP level
Secondary outcomes Attitudes related to TIC Well-being	School staff	Multi-level model	Pre-treatment scores of outcomes at staff level
Secondary outcomes Staff retention Staff sickness Exclusions & suspensions of CYP School attendance of CYP	School	Linear regression (OLS)	Pre-treatment scores of outcomes at school level

Sub-group analysis

The sub-group analysis will be twofold. First, we will conduct a latent class analysis (LCA) on the intervention group to explore whether there are emerging sub-groups with differential effects. LCA refers to the model whose underlying indicators are all categorical while for the continuous case, LCA is known as latent profile analysis (LPA) (Sinha, Calfee, & Delucchi, 2021). The LCA model will include the socio-demographic variables (sex, ethnicity, FSM) together with primary and secondary outcomes. This will allow us to observe 'latent' groups emerging from the data.

Second, we will conduct multilevel model by sub-groups considering a model with interaction may be more demanding in terms of power analysis. However, we will also consider for robustness check a multilevel model with interaction between treatment and sub-group dummy variable.

Missing data

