2.3.1 Primary outcome analysis

The primary outcome combines the Conduct Problems and Hyperactivity sub-scales of the Strengths and Difficulties Questionnaire (SDQ) to measure externalising behaviours.

We will employ a two-level multilevel model to account for the clustered nature of our data, where students are nested within schools. This modelling approach assumes that the schools included in the study represent a random sample from the broader population of schools. Multilevel models are well-suited for analysing hierarchical data structures and appropriately handling the variability within schools (among students) and between schools in terms of

outcomes. These models can effectively capture and model the complex sources of variation at multiple levels of the hierarchy (Bosker & Snijders, 2011).

The two-level **random-intercept model** is described by:

$$Y_{ij} = \beta_1 + TISUK_j\tau + (Baseline_{ij})\beta_2 + FSM_j\beta_3 + \mu_j + \varepsilon_{ij}$$

- Y_{ij} is the outcome for pupil i in school j ;
- $TISUK_j$ is a binary variable denoting whether a school is assigned to the intervention (1) or the control (0);
- $Baseline_{ij}$ represents pupil-level pre-test covariates and demographic characteristics at baseline for pupil i in school j .
- FSM_j is a binary indicator denoting whether a school is above the median proportion of FSM6 (1) or below (0).
- μ_j are the school level residuals [$\mu_j \sim i. i. d N(0, \sigma_\mu^2)$]
- ε_{ij} are the individual level residuals [$\varepsilon_{ij} \sim i. i. d N(0, \sigma_\varepsilon^2)$]

This is a random intercept model because $\beta_{1j} = \beta_1 + \mu_j$ corresponds to the school-level intercept for school j and $\beta_{1j} \sim i. i. d N(\beta_1, \sigma_\mu^2)$. The total variance is decomposed into two portions: the between-school variance (μ_j) and the within-school variance (ε_{ij}). The target parameter of the intervention is the average effect on pupil outcomes captured by τ .

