2.3.4 Further analysis

Additional analysis will be conducted at baseline after randomisation to check the balance between arms and at the follow-up stage. Incorporating the proportion of pupils with FSM status in the randomisation mechanism is designed to improve the balance across arms. After baseline testing, the evaluation team will check balances across arms. If, by chance, randomisation had not achieved the desired balance on those key socio-demographic characteristics that may affect outcomes, we may consider a multilevel analysis of covariance (ML-ANCOVA) as an additional model to test the robustness of our results. Nevertheless, if the randomisation incorporates % of FSM, it is unlikely that there is an imbalance across arms on FSM.

Stepwise regression analysis will be performed to model the relationship between pre-randomisation factors and demographics on observed outcomes at 15 months. Interaction terms with the allocation arm will be included in the analysis, and a significance level of 0.1 will be used to determine which factors are to be included in the regression model. Pre-randomisation factors will include pupil sex, FSM status and ethnicity. This analysis will be augmented by an additional analysis including participants in the intervention arm using the same pre-randomisation factors, process measures of intervention delivery, and staff changes in perceptions of trauma-informed care (this is for the regression analysis at school staff level).

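### The intervention-arm regression of outcomes on delivery does not name the baseline score as a covariate, so a non-randomised contrast may be confounded by a school's starting level

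*SAP*

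**What the plan says.** SAP 2.3.4 describes a stepwise regression "on observed outcomes at 15 months". It names the covariates: "Pre-randomisation factors will include pupil sex, FSM status and ethnicity". On selection it says that "a significance level of 0.1 will be used to determine which factors are to be included in the regression model". It then adds "an additional analysis including participants in the intervention arm using the same pre-randomisation factors, process measures of intervention delivery", together with staff changes in perceptions of trauma-informed care. The sentence closes with a parenthesis, "this is for the regression analysis at school staff level".

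Protocol 4.1 gives the same three factors and the same added analysis, "using the same pre-randomisation factors, process measures of intervention delivery, and staff changes in perceptions of trauma-informed care", but without the parenthesis.

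Baseline adjustment is stated elsewhere:

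- The baseline term of the primary model in SAP 2.3.1 "represents pupil-level pre-test covariates and demographic characteristics at baseline".
- SAP Table 5 lists pre-treatment scores for pupil, staff and school outcomes.
- SAP 2.3.2 carries the adjustment into the secondary outcomes.
- SAP 2.2 intends mean-centred baseline scores at pupil and school level in the multilevel models.

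**The concern.** In the randomised comparison, leaving out the baseline score mainly costs precision. Within the intervention arm it can do more harm, because the comparison is between schools that took up more of the programme and schools that took up less, and nobody randomised that.

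The protocol itself expects uptake to depend on the school. Section 2.3 has consultants working on barriers particular to each school. The case studies in section 5.2 examine leadership, size and demographics as influences on implementation. The risk table in section 11 lists implementation difficulties and changes of leadership. A link between delivery and the school's initial level of behaviour problems is therefore plausible, in either direction. If schools with more problems engage less, good delivery would look beneficial even with no effect. If they engage more, it would look harmful.

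The baseline score is the most direct measure of that starting level. It is collected before allocation, yet it is missing from the factors named.

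**Working it through.** The documents give no figure for this analysis, so there is nothing to reproduce. The steps below first establish the omission and then illustrate its possible size.

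**1. Is baseline adjustment supplied elsewhere?** SAP 2.3.1, 2.3.2 and Table 5 attach it to the primary and secondary outcome models. SAP 2.2 attaches it to the multilevel models in the context of the detectable effect size. SAP 2.3.6 says that the follow-up outcome analysis follows 2.3.1 and 2.3.2. None of these mentions the regression in 2.3.4, which has its own covariate list.

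**2. Inputs for the illustration.**

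- From the SAP: baseline ICC 0.015 (Tables 4 and 8, Randomisation column); baseline SD 4.37 for the intervention arm (Table 6); 40 intervention schools randomised, of which 4 dropped out, leaving 36 (section 2.2 and Table 4).
- Assumed, because the documents give no value: correlation r between delivery and the school's baseline level; school-level baseline-to-follow-up correlation b; 180 pupils per school; pupil-level pre–post correlation 0.6; the same ICC at follow-up; no true effect of delivery; sex, FSM status and ethnicity left out.

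**3. Spurious slope.** Per SD of delivery, in pupil SD units, it is r × b × √ICC.

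- √0.015 = 0.122 SD, or 0.122 × 4.37 ≈ 0.54 SDQ points between schools.
- With r = 0.3 and b = 0.8: 0.3 × 0.8 × 0.1225 = 0.029 SD, and 0.029 × 4.37 ≈ 0.13 points.
- Range for r from 0.1 to 0.5 and b from 0.5 to 0.9: 0.006 to 0.055 SD.
- For an even good-versus-poor split with the same correlation, the contrast is twice the slope: 0.012 to 0.110 SD, or 0.05 to 0.48 points.

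**4. False-positive rate by hand, 40 schools, r = 0.3, b = 0.8.** The variance of a school mean is 0.015 + 0.985/180 = 0.0205, so its SD is 0.143. The delivery–outcome correlation is 0.0294/0.143 = 0.205. The expected t is 0.205 × √38 / √(1 − 0.205²) ≈ 1.29. Against a critical value of 2.02, the rejection probability is about 23%.

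**5. Simulation of school means (4,000 runs per cell, nominal 5%).**

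| Schools | r | b | Without baseline mean | With baseline mean |
|---|---|---|---|---|
| 40 | 0 | 0.8 | 5.0% | 5.2% |
| 40 | 0.2 | 0.8 | 13.9% | 5.2% |
| 40 | 0.3 | 0.5 | 12.9% | 5.3% |
| 40 | 0.3 | 0.8 | 25.2% | 5.0% |
| 40 | 0.5 | 0.8 | 59.3% | 5.2% |
| 36 | 0.3 | 0.8 | 22.8% | 5.1% |

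A separate simulation with 150 pupils per school, 36 schools, r = 0.3 and b = 0.8 gave 21.7% without the baseline mean and 5.4% with it.

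**The case against.** **The list may not be complete.** The SAP speaks of pre-randomisation factors together with demographics and says that the factors will include three, all of them demographic. A baseline score is itself a pre-randomisation factor, and SAP 2.2 shows that the team means to use baseline scores at both levels. This stands in part. A reader might infer that the plan excludes baseline adjustment here, and the text does not support that. It supports only that the score is not named and that the general intention is not expressly extended to this regression.

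**The parenthesis about staff level may govern the whole added analysis.** If so, the missing covariate is the staff baseline score, the three pupil factors fit poorly, and the pupil ICC used above does not apply. If it governs only the staff-perception term, the pupil reading stands, and the listed pupil factors favour that reading. The text does not settle it. On either reading, change in staff perceptions is a regressor and does not adjust for the baseline of the outcome.

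**The plan makes no causal claim for this regression.** A reader might infer that it will be used to define successful delivery. That language belongs to the compliance analysis in SAP 2.3.9, which uses randomised assignment as an instrument. SAP 2.3.4 speaks only of a relationship.

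**The error rates are assumption-driven.** This is correct. The correlation and the stability are invented for illustration. Leaving out sex, FSM status and ethnicity probably overstates the bias to the extent that they carry school deprivation. The return to about 5% after adjustment follows from the setup, in which baseline level is the only confounder.

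**Conclusion.** The point holds as a gap in a stated covariate list. Run as written, a non-randomised delivery contrast would omit its most direct measured confounder.

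Under the central assumptions (ICC 0.015, r = 0.3, b = 0.8, other covariates ignored), the bias is about 0.03 SD, or 0.13 points on a 0–20 scale, per SD of delivery. The false-positive rate is roughly 20–25% at nominal 5%. The size depends on a delivery–baseline correlation that the documents do not give, and with zero correlation there is no bias. Only near the upper end of the range does an even-split contrast reach the trial's own detectable effect of 0.094.

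A reader might infer that the trial's main result is at risk. It is not: the randomised primary comparison adjusts for baseline and does not use this regression, and neither document ties a decision to it. Low severity; a free improvement.

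**What to change.** In SAP 2.3.4:

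1. State whether the added analysis is at pupil or staff level, and what the closing parenthesis covers.
2. Include the individual baseline score of the outcome analysed, its school mean and the FSM6 stratum, with a random intercept for school. The school mean is needed because the confounding arises between schools.
3. Force these terms in, outside the selection at 0.1, which could otherwise drop them.
4. State how missing baseline scores are handled. SAP 2.3.8 provides imputation only for missing outcome values, so there is no rule to borrow. Table 6 shows 1,983 missing in the intervention arm beside 7,214, about 22% of 9,197 if 7,214 counts the pupils with a score.
5. Report the result as an association. Unmeasured school features such as leadership and capacity remain.

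The cost is a few sentences and no new data collection. The missing-baseline rule is the only part that needs thought. Precision should also gain: in the 150-pupil simulations, with stability of 0.6 to 0.8, the standard error was 8–30% smaller with the school baseline mean in the model.

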2.3.5 Interim analyses and stopping rules

There are no interim analysis or stopping rules.

2.3.6 Longitudinal follow-up analyses

There is one follow-up analysis at the end of the intervention for all outcomes, 15 months after randomisation, which follows the outcome analysis described above in sections 2.3.1 and 2.3.2.

2.3.7 Imbalance at baseline

We have employed a minimisation approach to randomisation, which aims to balance the groups by considering the percentage of students eligible for free school meals (%FSM6¹¹) at the school level. The minimisation method incorporates %FSM6 as a stratifying factor, ensuring that schools with similar levels of FSM6 are evenly distributed across the control and intervention conditions. While a meticulously executed randomisation process does not guarantee perfect baseline balance, particularly for smaller sample sizes, it increases the likelihood of achieving comparable groups at baseline, as Glennerster and Takavarasha (2013) posited. Given the randomised assignment of schools, any remaining imbalances in baseline characteristics between the groups are expected to be due to chance rather than systematic factors.

Table 6 shows descriptive statistics from the study sample at baseline for the primary outcome and the variable at the school level used for randomisation.

Table 6 Baseline sample balance

School-level (categorical)	Control group		Intervention group		
	n/N (missing)	Count (%)	n/N (missing)	Count (%)	
FSM6>Median	38	19 (50%)	40	20 (50%)	
Pupil-level (continuous)	n/N (missing)	Mean (SD)	n/N (missing)	Mean (SD)	Effect size difference
SDQ - Conduct Problems and Hyperactivity sub-scale	6,179 (2,232)	7.46 (4.25)	7,214 (1,983)	7.62 (4.37)	0.00

¹¹ This refers to the situation when a student holds a historical FSM status. Following their FSM eligibility end date, they will retain the “Ever 6 FSM” classification for the subsequent six years. To illustrate, if a student was eligible for FSM from 1st September 2018 until 31st October 2020, their Ever 6 FSM status will continue until 31st October 2026, encompassing a 6-year duration beyond their FSM end date.

2.3.8 Missing data

The proportion of missing data and patterns of missingness will be examined for the primary outcome only, externalising behaviour at six months post-randomisation. Levels of missing data will be reported along with any systematic occurrences of missing data observed in the dataset.

In trials, some participants are inevitably lost to follow-up. The sample size estimation assumed that 20%¹² of participants would not provide an evaluable 6-month follow-up assessment. We will explore the mechanism of missing data to establish whether the data can be considered missing completely at random or missing at random. For each arm, we will present baseline data for those who were followed up at 6 months and those who were lost to follow-up. A logistic regression analysis will be conducted to explore any systematic differences between the allocated groups. If the regression model does not identify any predictor variables, it suggests that the missing data can be considered missing at random.

To avoid loss of efficiency, missing outcome values will be imputed using multiple imputation if the proportion of missing data is greater than 5% and less than 40%. When less than 5% of data is missing, the proportion is considered negligible, and missing observations will be excluded. Multiple imputation methods may perform less well when a substantial amount of data is missing (e.g., more than 40% for the primary analysis). In such cases, the assumptions underlying the imputation become less plausible, and the interpretative limitations of the trial data will be discussed in the results section.

An initial variable reduction analysis will explore the relationship between all potentially prognostic baseline variables and whether a follow-up data point is missing. Only variables where there is an association (p-value > 0.10) will be included in the imputation model.

The number of imputations will be determined to ensure at least 96% statistical efficiency (RE), according to the formula below, where l is the fraction of missing values and M is the number of repetitions:

$$RE = \left(1 + \frac{\lambda}{M}\right)^{-1}$$

¹² This accounts for 10% attrition and 10% non-consent rate

The statistical model and assumptions made in the analysis of the primary outcome will also be implemented in the multiple imputation procedures. If it is suspected that data is missing not at random or if the pattern of missing data is associated with trial allocation, sensitivity analysis will be performed using a pattern mixture approach with mixed modelling and multiple imputation to compare the sensitivity of conclusions to varying assumptions about the missing value mechanism.

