The evaluation team will complete the necessary protocol and prepare important documents for school recruitment, such as the MoU and opt-out letters for staff to distribute to parents/carers. We will also develop data collection tools, semi-structured interview topic guides and observation protocols.

The MoU will set out the expectations for participating schools. By entering into this agreement, schools that join the intervention and receive the treatment are unable to opt-out of the evaluation. In other words, delivering the intervention automatically entails joining the evaluation as well. The MoU stresses that the school staff are expected to commit to completing the staff outcome surveys as a fundamental part of signing up for the trial.

All the documents related to the research design and data collection activities will be submitted for ethics approval to the University of Kent ethical committee.

Recruitment

During this phase, TISUK will collect expression of interest from potential schools within eligible areas and collect signed MoUs from schools who meet the inclusion/exclusion criteria. More detail on the recruitment process is given in sections 3.3.

Baseline assessment

Baseline assessment will be conducted on all schools that are recruited into the trial before each school is allocated to intervention or control arm. Section 4 below describes the baseline measures and timing of data collection.

Randomisation

Eligible schools for randomisation (recruited by the delivery team) will be randomly assigned one of two groups, and implementation will commence. More detail on the randomisation process is given in section 3.4 below.

In the intervention phase (January 2023 – February 2025), schools in the intervention group will actively participate in the TISUK programme and implement the structural changes, while schools in the control group will continue BAU.

The evaluation team will monitor adherence to the intervention in schools within the intervention arm and BAU in the control group. More detail on compliance and monitoring adherence is provided in section **Error! Reference source not found.** and 5.

The post-intervention phase (March 2025 – September 2025) consists in three main activities:

- Outcome assessment
- Data analysis and reporting
- Data archiving

Outcome measurement

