2.1 Design overview

This efficacy trial adopts a two-arm, two-level design with pupils clustered into schools. The unit of randomisation is the school. All pupils in Year 8 in the participating schools undertake baseline tests from November 2023 to January 2024 and outcome tests at the follow-up stage in March 2025. The schools within the control group continue to function according to business-as-usual. There is no waitlist design in this trial.

The randomisation process adopts the minimisation approach considering whether the percentage of students eligible for free school meals (FSM6) at each school fell above or below the median percentage of FSM6 across all schools in the sample. More detail is discussed in the next section.

The randomisation process was executed by colleagues from the University of Kent, operating independently from the evaluation team at Ipsos UK. The University of Kent was provided with a list of schools without school names but marked with ID codes, ensuring they could not discern the schools' identities, thus maintaining blindness during the randomisation procedure. The randomisation procedure occurred in two phases: one in early December 2023 and another in January 2024. Initially, the intention was to conduct baseline testing for

all schools in November and proceed with randomisation in December. However, extending the timeline became imperative to accommodate additional time for recruitment, data collection, fieldwork, and the constraints posed by the Christmas break and Ofsted inspections, allowing schools ample opportunity to implement the surveys.

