2.2 Sample size calculations overview

Table 4 describes the minimum detectable effect size (MDES) estimates and sample sizes for the TISUK impact evaluation. The goal was to adopt conservative assumptions to allow for a well powered statistical analysis sufficient to detect an MDES below 0.20¹ and sub-population analysis.

Sample size estimations and assumptions

The goal is to calculate the required sample size for detecting a meaningful difference in the primary outcome measure of adolescent externalising behaviours. Key parameters involved in the calculation include the effect size, power, alpha level, and accounting for the clustered

¹ All YEF evaluations require a minimum detectable effect (MDES) below 0.20

design. Table 4 describes the sample size calculated using Stata 17© according to the following assumptions:

1. A pre-post zero correlation is assumed for externalising behaviours, as there are no reliable sources from which to base an estimate. Furthermore this represents the most conservative scenario for sample size estimation. Assuming a non-zero correlation would risk underestimating the required sample size if the assumed correlation is too high, we obtain a conservative sample size estimate for a covariance analysis by omitting this parameter and assuming a zero correlation. .
2. The SDQ (externalising scale) adolescent population mean is 6.0, and the assumed pooled Standard Deviation (SD) is 1.74², using the UK self-report population norms for 11-15 year olds³. Thus, to detect an effect size of 0.2 or greater, we need an SDQ externalising behaviours score difference of 6.0 (control) versus 5.66 (intervention). This difference requires 527 participants in each group, 1,054 for the whole sample.
3. Assuming 10% pupil-level attrition between baseline and follow-up requires a total sample size of 1,172.

Sample Size Calculation

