⁶ Average school size in England is 986, average year size is 200 and accounting for a potential 20% not consenting, hence, cluster size 160.

⁷ This is the actual cluster average size

⁸ Although the initial plan was to allocate schools equally to the intervention and control groups at the randomisation stage, the achieved sample showed a slight difference due to attrition during the recruitment

		Protocol	Randomisation
Number of participants	intervention	8,000	6,391
	control	8,000	7,214
	Total	16,000	13,393 ⁹

The MDES calculations were performed using PowerUp! Tool, developed by Dong and Maynard (2013), which incorporates the formula below according to Bloom, Richburg-Hayes, and Black (2007), for the two-level cluster randomised controlled trials:

$$MDES = M_{n-k*-2} \sqrt{\left(\frac{\rho(1 - R_C^2)}{P(1 - P)J}\right) + \left(\frac{(1 - \rho)(1 - R_i^2)}{P(1 - P)Jm}\right)}$$

Employing this formula enables the inclusion of baseline covariates at the cluster (school) level, pupil level, or both. Our analysis strategy intends to use mean-centered baseline scores within the multilevel models at both the pupil and school levels. Incorporating a covariate at both levels - school and pupil - enhances the trial's precision, resulting in a reduced Minimum Detectable Effect Size (MDES) estimate compared to methodologies that employ only one covariate or none.

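### The SAP's regression of missingness on trial arm names no adjustment for school, so its p-value for arm would be too small if run as written

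*SAP*

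**What the plan says.** On design, SAP 2.1 states: "The unit of randomisation is the school". Protocol section 4 has schools administer the survey to Year 8 in class-sized or smaller groups. SAP 2.2 records that four of the 78 randomised schools have since dropped out, all from the intervention arm.

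On missing follow-up of the primary outcome, SAP 2.3.8 plans: "A logistic regression analysis will be conducted to explore any systematic differences between the allocated groups". It then reads the result as evidence on mechanism: "If the regression model does not identify any predictor variables, it suggests that the missing data can be considered missing at random". Later in the same section, "if the pattern of missing data is associated with trial allocation, sensitivity analysis will be performed using a pattern mixture approach". Imputation variables are chosen by a separate variable-reduction step based on p-values, for which no model is named.

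Where the SAP means to handle clustering, it says so: random school intercepts for the pupil and staff outcomes (2.3.1, 2.3.2) and clustered standard errors for the CACE analysis (2.3.9). Section 2.3.8 carries the primary model into the multiple imputation, but not into the missingness regression.

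**The concern.** A missed session, a missed class or a lost school removes many pupils at once, so missingness will very probably cluster by school. Arm is constant within school. A regression that treats pupils as independent then understates the standard error for arm, just as it would for the outcome.

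Two things are at stake. One is the trial's statement on whether attrition differed by arm, which readers use to judge the primary result. The other is the condition that sets off the pattern-mixture analysis: if it responds mainly to chance variation among 78 schools, it says little about loss linked to allocation.

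**Working it through.** **Inputs.** Schools: 40 intervention, 38 control (SAP Table 4). Pupils per school: 166 (Table 4, whose footnote says "This is the actual cluster average size"). Expected missingness of 20% (SAP 2.3.8: "The sample size estimation assumed that 20"% would have no evaluable follow-up). The ICC of missingness is not given anywhere, so a range of 0.01 to 0.30 is assumed. For comparison, the outcome ICC is 0.03 as planned and 0.015 as observed at baseline.

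**The plan's own clustering figure.** SAP 2.2 states: "Assuming 10% pupil-level attrition between baseline and follow-up requires a total sample size of 1,172". 527/0.90 rounds up to 586 per group, or 1,172. The design effect is 1 + 0.03 × 160 = 5.8, and 1,172 × 5.8 = 6,797.6, which matches the stated 6,798. The plan therefore already accepts a substantial design effect for school-clustered pupil data.

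**False-positive rate of an unclustered test of arm.** With design effect DE = 1 + (166 − 1) × ICC, a nominal 5% test rejects with probability 2 × [1 − Φ(1.96/√DE)] when there is no arm effect. This was checked by simulation: 40 v 38 schools of 166 pupils, 20% missing, beta-distributed school rates, 3,000 runs per setting. The last column is a t-test on school-level missingness rates.

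| Assumed ICC | DE | Formula | Simulated, unclustered | Simulated, school-level |
|---|---|---|---|---|
| 0 | 1 | 5% | 5.6% | 5.1% |
| 0.01 | 2.65 | 23% | 23% | 5.1% |
| 0.03 | 5.95 | 42% | 42% | 4.7% |
| 0.05 | 9.25 | 52% | 53% | 5.0% |
| 0.10 | 17.5 | 64% | 64% | 4.6% |
| 0.20 | 34.0 | 74% | 75% | 5.3% |
| 0.30 | 50.5 | 78% | 78% | 4.8% |

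The rate passes one half when 1.96/√DE = 0.674, that is DE ≈ 8.4 and ICC ≈ 7.4/165 = 0.045.

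**Whole-school loss.** Four schools lost completely, with 10% to 20% of pupils lost elsewhere, imply an ICC of about 0.32 to 0.17. Simulating four schools lost at random plus 10% elsewhere gives 63% false positives unclustered and 7.6% for the school-level t-test. For the observed pattern, 4/40 v 0/38, a two-sided Fisher test on schools gives p = 0.12. Assume instead that those four schools return no follow-up and 10% of pupils are lost elsewhere. Missingness is then 0.10 + 0.90 × 0.10 = 19% v 10%, and the pupil-level z is 0.09/0.00621 = 14.5.

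**Illustration from Table 6 (baseline, not the planned follow-up test).** Taking n as valid responses, non-response is 2,232/8,411 = 26.5% in control and 1,983/9,197 = 21.6% in intervention. Unclustered, z = 7.7. The average is 17,608/78 = 225.7 pupils per school. At ICC 0.10, DE = 1 + 224.7 × 0.10 = 23.5, z = 7.73/4.84 = 1.60 and p = 0.11. At ICC 0.05, p = 0.027. The gap stops being significant at 5% from an ICC of about 0.065. Protocol 3.2 says of this measurement: "Baseline assessment will be conducted on all schools that are recruited into the trial before each school is allocated to intervention or control arm".

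**The case against.** The SAP does not say that the regression is unclustered. It calls it exploratory and sets no significance level for arm. That is fair: an ordinary regression is inferred from silence. But the SAP names clustering in its other models, and a plan should name it here too.

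A reader might infer that Table 6 already shows the planned test failing. It does not. Section 2.3.8 concerns follow-up, and no test of baseline non-response is planned. The counts are also unsettled: Table 4 gives 7,214 to control and 6,391 to intervention (sum 13,605, against a printed total of 13,393), while Table 6 gives 7,214 to intervention and 6,179 to control. If n in Table 6 included the missing pupils, the rates would be 36.1% v 27.5% and the ICC needed for non-significance about 0.17. Protocol 3.3 has baseline testing run into January, alongside the second randomisation batch, so strict ordering is not certain for every school.

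A reader might also infer that one regression drives the mechanism judgement, the trigger and the imputation screen. The SAP does not say that its p-value decides the trigger, though it names no other test; suspected missingness not at random is an alternative trigger. The screen is a separate step. As printed it keeps variables with p above 0.10, so understated p-values would exclude variables rather than admit them.

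Finally, a false positive leads to an additional sensitivity analysis, which is the cautious direction. Protocol 4.1 already plans pattern-mixture and multiple-imputation analyses when missing data exceed 5%, and 20% is expected. This limits the harm. It does not correct the standard error in the attrition comparison.

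**Conclusion.** The point holds as a gap in specification with a sizeable effect on one reported comparison. If the regression is run without a school term, a nominal 5% test of arm has a false-positive rate of about 23% to 78% for missingness ICCs of 0.01 to 0.30 at 166 pupils per school. The ICC is an assumption throughout. A claim that a false arm difference would be reported most of the time needs an ICC above about 0.045, which the documents do not establish.

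The harm is confined to the attrition statement and the pattern-mixture trigger; it would be wrong to infer a biased primary estimate. Nor do the four lost schools settle the matter. Their one-sided loss may be real, and p = 0.12 from 78 schools is weak evidence rather than evidence of no difference. The unclustered test would turn it into apparent near-certainty.

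**What to change.** In SAP 2.3.8:

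- Specify a multilevel logistic regression with a random school intercept (for example `melogit missing arm fsm covariates || school_id:`), or logistic regression with school-clustered standard errors, for the arm comparison.
- Use the same adjustment in any p-value screen of imputation variables, and correct the direction of the printed 0.10 threshold.
- Report whole-school loss by arm separately from pupil non-response within responding schools.
- Do not let a non-significant clustered p-value switch off the pattern-mixture analysis. Keep the rule in Protocol 4.1 of running it when missing data exceed 5%.
- Reconcile the arm counts in Tables 4 and 6 before any missingness rate by arm is quoted.

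The cost is a few sentences and one changed Stata command, with no new data. The downside is less extreme missingness p-values and slightly more reporting.
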